5.3. Method of Assignment to Treatment

Patients who meet all criteria for enrollment will be randomly assigned in a $1:1:1$ ratio to receive treatment on LY2157299 monotherapy, LY2157299 plus lomustine therapy, or lomustine plus placebo therapy using an interactive voice-response system (IVRS). This will occur before Cycle 1 Day 1. There is no plan to have an unblinded site representative for this study.

A dynamic allocation method, introduced by Pocock and Simon (1975) (and extended for unequal treatment group sizes by Han et al. [2009]), will be adopted to minimize imbalance between treatment arms according to the following factors:

- baseline ECOG PS (0, 1)
- age (≤ 60 , > 60 years)

- GB, primary or secondary at study entry

The randomization parameter P will be set at 0.9 to maximize the benefit of the allocation procedure, while keeping treatment assignments unpredictable. Randomization will be monitored periodically and the randomization parameter will be modified if necessary.

6. A Priori Statistical Methods

6.1. General Considerations

Statistical analysis of this study will be responsibility of both PharmaNet/i3 (under the direction of Eli Lilly and Company) and Lilly.

Patients from all sites will be pooled for the purposes of analysis. Inference about survival will be made using a Bayesian posterior probability for the superiority of LY2157299 plus lomustine arm survival over lomustine plus placebo arm. The remaining analyses of this study will estimate differences between arms where appropriate, including exploratory analyses. Descriptive statistics by treatment arm will also be provided.

Results of descriptive analyses and estimates from inferential analyses will be presented by treatment arm. For continuous variables, summary statistics will include number of patients, mean, median, standard deviation, minimum, and maximum. Categorical endpoints will be summarized using number of patients, frequency, and percentages. Any missing longitudinal data will not be imputed, rather estimated from an appropriate random mixed effects model. Transformations will be applied where assumptions behind any analysis are better satisfied by data being transformed onto an alternative scale. All results from any of these analyses will be back transformed to the original scale. Alternatively, nonparametric methods will be applied.

Any change to the data analysis methods described in the protocol will require an amendment ONLY if it changes a principal feature of the protocol. Any other change to the data analysis methods described in the protocol or additional exploratory analyses deemed appropriate, and the justification for making the change and additions, will be described and justified in the statistical analysis plan and/or clinical study report. The following terms and data handling conventions will be used in the analysis.

Table JBAL.6.1. Data Definitions and Rules

Term	Definitions or Rule
Entered	Patients who have signed the informed consent document directly.
Screen failures	Patients who have signed informed consent, do not meet eligibility criteria and are not randomized.
Randomized/ Enrolled	Patients who have been assigned to study treatment and but may have not received any study treatment (LY2157299, LY2152799-matched placebo, or lomustine).
Patients on therapy	Patients who have been randomized/enrolled to study treatment and have received at least 1 dose of study treatment (LY2157299, LY2152799-matched placebo, or Lomustine).
Study day	If assessment is on or after date of first LY2157299/ LY2152799-matched placebo dose then (date of assessment) – (date of first study treatment dose) + 1 If assessment precedes first treatment dose then (date of assessment) – (date of first study treatment dose)

	There is no study day 0. Study day 1 is the date of first dose and study day -1 is the day before the first dose.
Cycle day	If assessment is on or after date of first LY2157299/ LY2152799-matched placebo dose then (date of assessment) – (date of first study treatment dose in cycle) + 1 If assessment precedes first treatment dose then (date of assessment) – (date of first study treatment dose in cycle) There is no cycle day 0. Cycle day 1 is the date of first dose in the cycle and cycle day -1 is the day before the first dose.
Baseline	For change from baseline analysis, baseline value is defined as the last reported measure on or before the first dose date (or discontinuation, if no treatment is given). For change from baseline within a cycle, the measure prior to the first dose if that cycle is baseline.
Study treatment period	Time from treatment start to discontinuation from study treatment
Post-discontinuation – short-term follow-up	The short term follow-up period begins 1 day after discontinuation of study treatment and lasts approximately 30 days (Visit 801).
Post-discontinuation – long-term follow-up	The long-term follow-up period begins 1 day after the short-term follow-up period (Visit 801) is completed and continues until death to collect survival data.

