10.4.4. Samples for Drug Concentration Measurements Pharmacokinetics/Pharmacodynamics

Pharmacokinetic collection is critical for the evaluation of safety risks for patients receiving LY2157299. Hence, population PK sampling will be required in this study and combined with ECG evaluation.

Sparse blood samples (2 mL) for the measurement of LY2157299 used for PK/PD evaluation will be collected during Cycle 1 for each patient in the study (see [Attachment 1](#) and [Attachment 3](#)).

The actual time of dosing on the day of sampling and the actual time of sampling for each of the samples must be collected. Dose information (time and amount of LY2157299 dose recording in patient diaries) must be collected for the day of sampling and the 2 days prior to the sampling day. This information can be obtained from the patient diary at the visit for blood sampling.

Additionally, PK draws may be obtained for patients who show high variability of LY2157299. This is required to evaluate PK-related toxicity risks. Such PK draws will be discussed with the investigator and documented in the eCRF.

Instructions for the collection and handling of blood samples will be provided by the sponsor.

Plasma samples will be analyzed for LY2157299 using a validated method.

Bioanalytical samples collected to measure investigational product concentration will be retained for a maximum of 1 year following last patient visit for the study.

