Attachment 3. Pharmacokinetic Sampling

In conjunction with the Study Schedule of Events, the following PK draws will be conducted.

Sparse PK Sampling Schedule for Phase 2

Sample Number	Cycle	Day	Sampling Windows for plasma PK	ECG and ECG Chemistry	Optional CSF collection ^b
1	1	1	Predose ^a	X	
2	1	1	0.5 to 2 hours		0.5 hours ^b
3	1	1	3.5 to 5 hours	X	4 hours
4	1	3	Predose ^a	X	Predose
5	1	14	Predose ^a	X	Predose
6	1	14	0.5 to 2 hours		0.5 hours
7	1	14	3.5 to 5 hours	X	4 hours
8	1	15	Morning	X	Morning
9	1	16	Morning		

Abbreviations: CSF = cerebrospinal fluid; ECG = electrocardiogram; PK = pharmacokinetic.

^a The predose sample has to be taken before receiving any LY2157299 monohydrate.

^b CSF collection time as close as possible to plasma sample.

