6.13.4. Clinical Laboratory Evaluation

Listings of all laboratory results will be provided (using SI units [International System of Units], when available) by treatment, separately for hematology, chemistry, urinalysis, special chemistry, ECG chemistry, immune phenotype, whole blood for Fox3p, and urine C-terminal telopeptides of Type 1 collagen. Normal reference ranges, percent of the result outside of range (result divided by lower limit if result is less than lower limit; result divided by higher limit if result is greater than higher limit) and percent change from baseline will also be included.

A calculated CTCAE grade using CTCAE version 4 will be provided for all laboratory results which can be used independently of clinical judgment to determine a CTCAE severity grade. These summaries will be repeated for abnormal laboratory results.

The CTCAE term will be summarized by CTCAE grade in separate tables, linking these AEs to the laboratory term.

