6.13.6. Electrocardiograms

Electrocardiogram (ECG) assessment of normality and clinical significance will be listed by treatment group. Myocardial information and quantitative results including PR, QRS, QTcB (Bazett's correction), QTcF (Fridericia's correction) and RR intervals will be provided in patient listings. In addition, listings and summaries of outlying corrected QT intervals (QTc, QTcB and QTcF) will be provided for each scheduled time point.

Baseline ECGs are ECGs performed either during screening or predose during the study. Changes in QT from baseline, delta QT, will be calculated by subtracting the respective reading taken at the same nominal time during screening from the reading taken after LY2157299 dosing on specified days as per protocol schedule. Similarly, changes in RR from baseline (ie. delta RR) will be calculated. Delta QT will then be analyzed using a linear mixed-effects model with treatment arm, timepoint and delta RR as fixed effects, treatment-by-time interaction and patient as a random effect (Dmitrienko and Smith 2003). Least square means by timepoint and treatment arm together with 90% confidence intervals will be provided. Mean differences and 90% confidence intervals between treatment arms will be estimated from the model.

If data warrant, additional exploratory analyses may be conducted using appropriate modeling techniques.

The ECG chemistry laboratory values will be listed and summarized separately from other laboratory values.

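### The SAP's baseline rule goes by calendar date, so read literally it makes the 3.5–5 h post-dose ECG-chemistry sample on Cycle 1 Day 1 the baseline

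*SAP*

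**What the plan says.** The Baseline row of SAP Table JBAL.6.1 (section 6.1) holds two rules. For change from baseline in general, the "baseline value is defined as the last reported measure on or before the first dose date". The next sentence covers a different case: "For change from baseline within a cycle, the measure prior to the first dose if that cycle is baseline" (the printed 'if' reads as 'of').

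Protocol Attachment 3 has a column headed "ECG and ECG Chemistry". On Cycle 1 Day 1 it is marked at sample 1 (predose) and at sample 3 (3.5 to 5 hours). A footnote adds: "The predose sample has to be taken before receiving any LY2157299 monohydrate".

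SAP 6.13.4 lists laboratory results by treatment, names ECG chemistry among the panels, and says that "percent change from baseline will also be included". It gives no baseline of its own. SAP 6.13.6 sets a separate baseline for the tracings ("Baseline ECGs are ECGs performed either during screening or predose during the study"), but on the chemistry it says only: "The ECG chemistry laboratory values will be listed and summarized separately from other laboratory values".

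Protocol 8.1.1 defines the baseline period as running from screening to first study treatment.

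**The concern.** A date-based rule is harmless when a variable is measured once on the first-dose date, before dosing. ECG chemistry is measured twice on that date, and the later sample is on drug. The last measure on or before the date is then the post-dose one whenever the schedule is followed, so this is the ordinary case and not an exception.

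What is at stake is how the change-from-baseline figures for this panel read: lipase, thyroid tests, albumin, glucose, calcium, sodium, potassium, phosphorus and magnesium. A baseline that already contains an acute effect hides that effect at the matching post-dose time, and it can show a change in the opposite direction once the effect has gone. SAP 6.1.1 also limits laboratory analyses to patients with a post-baseline assessment. Under the literal rule, a patient whose only on-treatment ECG-chemistry draw is on Day 1 would have no post-baseline value for the panel.

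**Working it through.** The plan states no figure to reproduce. The check applies each rule to the schedule.

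**Inputs**
- First-dose date: Cycle 1 Day 1, the first day of LY2157299 or placebo. Lomustine starts on Day 7 (Protocol 8.1).
- ECG-chemistry samples: prestudy; Day 1 predose and 3.5–5 h; Day 3 predose; Day 14 predose and 3.5–5 h; Day 15 morning (Attachments 1 and 3). In later cycles, Day 26 (Attachment 1).
- Day 26 falls 12 days after the last scheduled dose of the cycle (26 − 14 = 12).

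**Which sample becomes baseline**
- General rule, by date: the last sample with date ≤ Day 1 is Day 1, 3.5–5 h.
- Rule with a before-first-dose time condition: Day 1 predose, or the prestudy value if that is missing.
- Within-cycle rule applied to Cycle 1: Day 1 predose.

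**Effect on the reported change**

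Let B be the predose value and d the acute effect at 3.5–5 h. The documents give no value for d, so it stays a symbol. Let k be the share of d present at the predose and morning samples, assumed to lie between 0 and 1. Take the effect to have gone by Day 26.

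Change under the date rule = (true change from predose) − d.

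| Sample | True change from predose | Change under date rule |
|---|---|---|
| Day 1, 3.5–5 h | +d | d − d = 0 |
| Day 14, 3.5–5 h, if the same effect recurs | +d | d − d = 0 |
| Day 3 predose, Day 14 predose, Day 15 morning | +kd | kd − d = −(1 − k)d |
| Day 26 of a later cycle | 0 | 0 − d = −d |

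For the third row, k = 0, 0.25, 0.5 and 1 give −d, −0.75d, −0.5d and 0, where the true changes are 0, +0.25d, +0.5d and +d.

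SAP 6.13.4 lists percent change, which under the date rule is 100 × (Y − (B + d)) / (B + d). It is 0 at Day 1, 3.5–5 h whatever d is. At an off-drug visit with Y = B it is −100d / (B + d), where the true figure is 0.

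With the time condition, or with the within-cycle rule in Cycle 1, both 3.5–5 h samples show +d and nothing cancels.

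**Overlap with routine chemistry**

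Attachment 2, footnote c, drops seven analytes from ECG chemistry when routine chemistry is due at the same time point: albumin, glucose, calcium, sodium, potassium, phosphorus and magnesium. Both panels are scheduled on Day 26 of later cycles. Routine chemistry is drawn prestudy and not on Day 1. If baselines are derived panel by panel, the routine-chemistry changes are unaffected. If they are derived by analyte across panels, the shift carries over to the shared analytes. The SAP does not say which.

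**The case against.** The strongest reply is that the same table row already gives a predose baseline for change within a cycle, and that every post-dose ECG-chemistry sample in Attachment 3 falls in Cycle 1. The intent elsewhere is also predose: Protocol 8.1.1 ends baseline at first treatment, ECG tracings use screening or predose, and Attachment 3 requires the predose draw. This stands as evidence of intent. It does not settle the matter, because SAP 6.13.4 speaks simply of change from baseline, which matches the date-based sentence, and nothing assigns ECG chemistry to the within-cycle rule.

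Other limits stand in full, and they rule out stronger conclusions that a reader might draw:
- **That all acute effects disappear from the safety results.** Cancellation is possible only at the two 3.5–5 h times, Days 1 and 14; other visits are shifted. Raw values, reference-range comparisons and calculated CTCAE grades do not use this baseline and would still show an acute abnormality.
- **That a between-arm comparison is biased.** ECG chemistry is only listed and summarized. No model, test or arm difference is specified for it.
- **That the accumulation ratio of about 1 (Protocol 5.6.5.1) proves full cancellation.** That ratio concerns plasma LY2157299. Similar exposure does not establish a similar effect on electrolytes, lipase or thyroid tests, and the documents report no acute effect on any of them.
- **That other Day 1 assessments suffer in the same way.** The other repeated items in Attachment 3 are ECGs, which have their own baseline, drug concentrations and optional CSF.

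The comments column of Attachment 1 is redacted and may bear on timing.

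**Conclusion.** The point holds within a narrow scope. As written, the general rule selects an on-drug value as the ECG-chemistry baseline, contrary to the protocol's own baseline period. The affected outputs are the percent-change listings and any change summaries for this panel. QT/RR analyses and overall survival are untouched.

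The size is 0 in place of +d on Day 1 at 3.5–5 h, about 0 in place of +d on Day 14 at 3.5–5 h, and a shift of −d in the absolute change elsewhere. The Day 1 result follows from the rule alone. The Day 14 result assumes that the same effect recurs, and the Day 26 result assumes that it has worn off. Because d is unknown and may be zero, the documents support a defect in the rule. They do not support a statement that a real effect will be lost.

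**What to change.** In the Baseline row of SAP Table JBAL.6.1, define baseline as the last non-missing measure before the date and time of the first dose of study treatment. If no time is recorded on Day 1, use the nominal predose sample; otherwise use screening. State that ECG-chemistry change from baseline uses this rule, and say whether baselines for analytes shared with routine chemistry are derived by panel or by analyte.

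The cost is a sentence or two in the SAP and a small programming change. Protocol 10.4.4 already requires for drug-concentration samples that "The actual time of dosing on the day of sampling and the actual time of sampling for each of the samples must be collected", and Attachment 3 pairs ECG chemistry with those samples. That clock times will also be recorded for the chemistry tubes is an inference, which is why the nominal-sample fallback is needed.

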6.1.1. Analysis Populations

Primary time-to-event efficacy analyses will be conducted on all randomized patients. This set will group patients according to their allocated treatment.

All patients who entered the study will have measurable disease. However, should a patient be required to undergo a surgery for palliative reasons before objective tumor progression he/she will be excluded from analyses and summaries associated with tumor response. Such cases, will not be common in this disease setting. This set will group patients according to their allocated treatment.

Safety analyses will be based on the safety population, defined as all randomized patients receiving at least 1 dose of any study drug. Patients will be grouped according to treatment received in Cycle 1. A subanalysis will be conducted by excluding patients who should have been otherwise discontinued to determine their influence on the final study results.

For all laboratory and biomarker assessments analyses, patients with at least one post-baseline assessment will be included for analysis. This set will group patients according to their allocated treatment.

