10.1.3. Primary Efficacy Endpoint

The primary efficacy endpoint is OS. Overall survival (OS) is defined as the time from the date of randomization to the date of death from any cause. For patients not known to have died as of the data cut-off date, OS time will be censored at the last contact date the patient was known to be alive prior to the cut-off date.

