12.2. Statistical and Analytical Plans

12.2.1. General Considerations

Statistical analysis of this study will be the responsibility of Eli Lilly and Company.

Time-to-event efficacy analyses will be conducted on all patients who received at least 1 dose of study drug treatment. This set will group patients according to their allocated treatment.

Only patients with measurable disease will be included in summaries of tumor response.

Safety analyses will be based on the safety population, defined as all randomized patients receiving at least 1 dose of any study drug. Patients will be grouped according to treatment received in Cycle 1. A subanalysis will be conducted by excluding patients who should have been otherwise discontinued to determine their influence on the final study results.

Patients from all sites will be pooled for the purposes of analysis. Inference about survival will be made using a Bayesian posterior probability for the superiority of LY2157299 plus lomustine arm survival over lomustine plus placebo arm. The remaining analyses of this study will estimate differences between arms where appropriate, including exploratory analyses.

Descriptive statistics by treatment arm will also be provided.

Results of descriptive analyses and estimates from inferential analyses will be presented by treatment arm. For continuous variables, summary statistics will include number of patients, mean, median, standard deviation, minimum, and maximum. Categorical endpoints will be summarized using number of patients, frequency, and percentages. Any missing longitudinal data will not be imputed, rather estimated from an appropriate random mixed effects model. Transformations will be applied where assumptions behind any analysis are better satisfied by data being transformed onto an alternative scale. All results from any of these analyses will be back transformed to the original scale. Alternatively, nonparametric methods will be applied.

Any change to the data analysis methods described in the protocol will require an amendment ONLY if it changes a principal feature of the protocol. Any other change to the data analysis methods described in the protocol or additional exploratory analyses deemed appropriate, and the justification for making the change and additions, will be described and justified in the SAP and/or clinical study report.

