6.5. Use of an “Efficacy Subset” of Patients

The efficacy analyses on time-to-event endpoints will be conducted on all patients who received at least 1 dose of any study drug. Patients that discontinued after randomization and did not receive study treatment for reasons other than not meeting entry criteria will be followed for survival till death occurs. Since the effect of the study drug is not realized in these patients, the time-to-event analyses will not include these patients.

Patients that did not meet entry criteria after receiving study treatment (for example, protocol violators) will be included in the main efficacy and safety analyses. However, a subanalysis will be conducted by excluding these patients who should have been otherwise discontinued to determine their influence on the final study results.

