- **Disease Control Rate** is defined as the proportion of patients who achieved a best response of CR, PR or stable disease (SD) per RANO criteria. This rate will be estimated for each treatment group by dividing the total number of patients that had CR, PR or SD by the number of patients who received at least 1 dose of study treatment. Best response of SD is defined as disease that does not meet the criteria for CR, PR, or progressive disease (PD) and has been evaluated at least one time, and at least 6 weeks after baseline assessment. Patients without a valid response assessment at least 6 weeks after baseline assessment are assigned a best response of nonevaluable unless progression has already occurred.

All primary and secondary efficacy endpoints will be analyzed for patients who received at least one dose of study treatment. All time-to-event endpoints will be analyzed using the Kaplan-Meier method. Covariates may also be included in these time-to-event models to account for variation in survival time. A Bayesian model will be used to estimate the hazard ratio of overall survival between the treatment arms.

Table JBAL.6.10. An Overview of the Efficacy Analyses

Efficacy Endpoint	Statistical Analysis	SAS Procedures
Primary analysis:		
Overall survival	A Bayesian OS model to estimate the hazard rates and ratios (HR) of OS and 90% predictive interval between LY2157299 plus lomustine therapy and lomustine plus placebo therapy	Non SAS - FACTS
Secondary analyses:		
Overall survival	
The same Bayesian OS model in the primary analysis is used in secondary analysis to estimate the HR between LY2157299 monotherapy and lomustine plus placebo therapy, and between LY2157299 plus lomustine therapy and LY2157299 monotherapy
 
Kaplan-Meier method will be used to estimate median survival time, OS rate at 12 months, and its 95% confidence interval for the treatment arms
 
Proportional hazard model will be used to estimate the hazard ratio of survival and 95% confidence interval between treatment arms, control for other factors
	Non SAS - FACTS
Progression-free survival	
Kaplan-Meier method will be used to estimate median PFS, PFS rates at CCI, and its 95% confidence interval for the treatment arms
 
Proportional hazard model will be used to estimate the hazard rate and ratio of PFS and 95% confidence interval of the 3 treatment arms and between the treatment arms
	LIFETEST

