6.10.4. Sensitivity Analyses

Additional analyses may be carried out to judge the influence of any patients who did not meet enrollment criteria but were inadvertently enrolled and continued on treatment after obtaining approval from the sponsor and/or patients who have continued treatment after objective disease progression. A subanalysis will be conducted by excluding such patients to determine their influence on the final study results.

Additional sensitivity analyses may also include the use of different censoring dates in the time-to-event analyses.

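### The primary overall survival population is not fixed: one SAP section uses all randomized patients, while two other SAP sections and the protocol use only dosed patients

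*SAP*

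**What the plan says.** Four unredacted statements set the population for the time-to-event analyses.

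- SAP 6.1.1 (Analysis Populations): "Primary time-to-event efficacy analyses will be conducted on all randomized patients", grouped by allocated treatment.
- SAP 6.5 (Efficacy Subset): "The efficacy analyses on time-to-event endpoints will be conducted on all patients who received at least 1 dose of any study drug". On patients who were randomized but never dosed it adds: "Since the effect of the study drug is not realized in these patients, the time-to-event analyses will not include these patients".
- SAP 6.10 (Efficacy Analyses): "All primary and secondary efficacy endpoints will be analyzed for patients who received at least one dose of study treatment".
- Protocol 12.2.1 (General Considerations): "Time-to-event efficacy analyses will be conducted on all patients who received at least 1 dose of study drug treatment", again by allocated treatment.

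The two sets can differ. SAP Table JBAL.6.1 defines randomized patients as "Patients who have been assigned to study treatment and but may have not received any study treatment", randomization takes place before Cycle 1 Day 1 (Protocol 9.3, SAP 5.3), and SAP 6.6 will report patients who died or discontinued before treatment began.

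The endpoint itself runs from randomization. Protocol 10.1.3: "Overall survival (OS) is defined as the time from the date of randomization to the date of death from any cause". The SAP 6.10 definition agrees.

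**The concern.** The trial is declared a success on one posterior probability compared with one threshold (Protocol 12.1 and 12.2.6, SAP 6.10.1). Once a single randomized patient goes undosed, that probability can be computed in two ways, each supported by a sentence in the plan. Nothing states which decides or requires both to be shown. SAP 6.10.4 does not help: it covers ineligible patients, treatment continued after progression, and censoring dates ("Additional sensitivity analyses may also include the use of different censoring dates"), but neither population. The choice could therefore be made after the data are known.

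The population may also affect which deaths count towards the event-based database lock; the text does not say. The secondary OS comparisons with the open-label monotherapy arm are more exposed than the blinded primary comparison, because patients can learn their allocation before the first dose. The documents give no undosed rate, so no direction of bias can be predicted.

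**Working it through.** **1. The texts side by side**

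| Place | Set | Names the primary endpoint? |
|---|---|---|
| SAP 6.1.1 | all randomized | yes |
| SAP 6.5 | at least one dose; undosed excluded | no, but covers time-to-event endpoints without exception |
| SAP 6.10 | at least one dose | yes |
| Protocol 12.2.1 | at least one dose | no, but gives no other time-to-event set |

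The heading of SAP 6.5 could suggest a supportive subset. SAP 6.10 rules that out by applying the dosed set to primary endpoints. With any undosed patient, the four statements cannot all be followed.

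**2. The plan's own figure**

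Protocol Attachment 10 gives 74% log-rank power at one-sided alpha 0.1. It cannot be reproduced, because the hazard ratio, events and allocation are redacted. It can be rescaled for an assumed undosed fraction x. The implied drift is 1.2816 + 0.6433 = 1.9249.

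- Dosed only: power = Φ(1.9249 × √(1−x) − 1.2816).
- All randomized, no effect in undosed patients: power = Φ(1.9249 × (1−x) − 1.2816).

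| x | Dosed only | All randomized |
|---|---|---|
| 1% | 73.7% | 73.4% |
| 2% | 73.4% | 72.7% |
| 5% | 72.4% | 70.8% |
| 10% | 70.7% | 67.4% |

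The gap is 0.3 to 3.3 points, so power is not the main issue.

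**3. How often the two sets disagree on success**

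Inputs from the documents:
- control median 8.5 months, so λ₀ = ln 2 / 8.5 = 0.0815 per month (Protocol 12.1);
- minimum follow-up 94 weeks, 21.6 months (Protocol 12.1);
- Gamma prior on the control hazard with weight w = 1 or 10 (SAP 5.2);
- a near-flat prior on the log hazard ratio, taken as flat (SD 100, SAP 5.2).

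Assumed inputs: 80 versus 40 patients, uniform accrual over 15 months, undosed median 3 months in either arm, undosed patients fully followed, 90% threshold. The possible hierarchical term is not modelled.

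With D deaths and E person-months in the combination (T) and control (C) arms,

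Pr(HR < 1) = cdf of Beta(D_T, D_C + w) at E_T / (E_T + E_C + w/λ₀).

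This was computed on both sets in each of 80,000 simulated trials per setting. Base case (w = 1):

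| Undosed | Opposite verdicts, HR 1 | Opposite verdicts, HR 0.7 | Success at HR 0.7, all randomized / dosed | Success at HR 1, all randomized | Success at HR 1 if either set may be used |
|---|---|---|---|---|---|
| 1% | 1.0% | 2.2% | 66.0% / 66.1% | 9.7% | 10.2% |
| 2% | 1.5% | 3.4% | 65.4% / 65.6% | 9.7% | 10.4% |
| 5% | 2.5% | 5.7% | 64.5% / 64.8% | 9.8% | 11.0% |

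The Monte Carlo standard error of a disagreement rate is at most 0.1 points.

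**4. Range over the assumptions**

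The grid used arms of 60/30, 80/40 and 90/45, undosed median 3 or 8.5 months, w = 1 or 10, and thresholds of 85%, 90% and 95%. The 90/45 case is an upper bound: 90 + 45 + 45 = 180, the number entered in the protocol synopsis, if the ratio were 2:1:1, which is itself an assumption.

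- Opposite verdicts: 0.4–2.5% (1% undosed), 0.7–3.9% (2%), 1.1–6.8% (5%).
- Rise in false success if the better set is picked afterwards: 0.2–2.1 points.
- Difference in average success: at most 2.5 points.

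**5. Is an undosed patient likely?**

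At an assumed 1% rate, the chance of at least one among 120 patients is 1 − 0.99¹²⁰ = 70%.

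**The case against.** The strongest reply is that the dosed set is the real rule and SAP 6.1.1 contains one stray sentence. Three of the four places use dosed patients. SAP 6.3 sends the reader to SAP 6.5 for handling early discontinuers, and SAP 6.5 is the only section that gives a reason for its choice. The SAP was based on the November 2011 protocol, and the amended protocol still uses the dosed set. A departure from protocol methods is supposed to be justified, and SAP 6.1.1 offers no justification. On this view, editing one sentence in SAP 6.1.1 would suffice, and asking for all randomized patients is partly preference. The primary model also borrows historical controls, so its inference does not rest on randomization alone. Finally, the effect is small under inputs that are all assumed, and nothing suggests anyone would pick the better result.

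Part of this stands. Either set would remove the contradiction, and the average effect is small. The rest does not settle the matter. The SAP 6.3 pointer concerns patients who stop treatment early and does not rank SAP 6.5 above SAP 6.1.1. The protocol's rule on changes cannot resolve a conflict inside the SAP, where 6.1.1 and 6.10 both speak of primary analyses. Counting sections is not a precedence rule.

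**Conclusion.** The concern holds. The primary OS population is stated in two incompatible ways in fully visible text, and no precedence is given. The conflict itself rests on no assumption; its size does, because arm sizes, allocation and threshold are redacted and the undosed rate is not given. Within the ranges examined, opposite verdicts are uncommon, average success hardly moves, and false success rises modestly, and only if the set were chosen with the results in view. It must still be corrected, because the quantity that decides the trial is not fully prespecified.

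**What to change.** **Main change.** State in SAP 6.5, SAP 6.10 and Protocol 12.2.1 that OS and PFS are analysed in all randomized patients by allocated arm, as SAP 6.1.1 already does. This set matches endpoints measured from randomization, Protocol 8.2's reliance on randomization for inference, and the statement in Protocol 8.1 and SAP 5.1 that survival is collected for all patients. Name the dosed-only analysis in SAP 6.10.4 as a sensitivity analysis, which meets the reason given in SAP 6.5. Settle this before any unblinded efficacy results are reviewed.

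**Secondary clean-up, lower priority.**

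- Response and disease control rates: the denominator is randomized patients in Protocol 10.1.4 (response rate only), Protocol 12.2.7 and SAP 6.10.3, but dosed patients in SAP 6.10 and Table JBAL.6.10. Use all randomized throughout. Reconcile the measurable-disease limit in Protocol 12.2.1 and the palliative-surgery exclusion in SAP 6.1.1 with that choice, for example by reporting the measurable-disease rate as supportive.
- Survival follow-up: SAP 6.5 promises it for patients undosed for reasons other than entry criteria and is silent on the rest. State that every randomized patient is followed.
- Measurable disease: the synopsis and SAP 6.1.1 say patients have it, while inclusion criterion [3] admits evaluable disease after resection. Reconcile these.

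**Cost.** Wording changes in SAP 6.5, 6.10, 6.10.4 and Table JBAL.6.10, and in Protocol 12.2.1. The protocol requires an amendment only for a principal feature; the primary population may count as one. There is some extra survival follow-up for ineligible undosed patients, whose number is not given, and the reported response rate may be slightly lower.
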